##### Families:

The consent process for families (in the intervention and control groups) was different than that for primary care providers. Families for whom ASD is suspected will be handed a study interest form by their PCP. The PCP will ask if they are interested in learning more about the study. If so, they will indicate their interest by completing a study interest form. This study interest form will serve as authorization to allow the PCP to release information to the researchers for recruitment purposes. This signed interest form signifies study interest but is not a consent for the study. Interested parents will then be contacted by the study team via phone, text or email, to secure electronic signed consent or verbal consent.

Text messaging, using the secure Twilio app hosted by OHSU, will be utilized for scheduling phone calls. Text messaging will not be used to obtain consent but will be used to schedule a phone appointment to obtain consent. After consenting, the family may also choose to receive text messages from the navigator or study team with updates, reminders, or other scheduling requests.

**Electronic consent:** Families will sign consent electronically through a form built in Research Electronic Data Capture (REDCap). The software allows consent forms to be emailed directly to the email address that the participant provides upon signing the Study Interest Form. Per OHSU OCTRI requirements, participants will click a radio-box for yes or no, and if yes is selected, will enter their first and last name. This will be used in conjunction with the timestamp on the REDCap form to confirm consent to the study. In most cases, participants will provide electronic consent while on the phone with a Navigator, who will be able to confirm their identity through phone, email, and signature congruency.

**Verbal Consent over the Phone:** For families lacking internet access, a verbal consent via telephone will be provided in lieu of electronic signed consent. For these families we have requested a HIPAA waiver/alteration.

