### ***Modifications to the Consent Process***

For the pilot, It should be noted that primary care sites are only obtaining authorization to share family contact information with the study team and not directly obtaining informed consent. Given the realities of community primary care (e.g., 15 to 20 minutes for an entire well child check), it is not possible for community primary care providers to obtain informed consent. In addition, doing so would require the study team to engage 30 community primary care providers in research, which it is unlikely that they would be consistently willing to do. Whenever possible, signed consent and authorization will be obtained electronically. However, we are requesting a waiver of consent documentation for families that cannot access the internet. This will allow us to obtain consent and authorization verbally for those individuals when it is not practicable to get signed consent and authorization. We have also submitted the necessary HIPAA documentation to allow for this verbal consent and authorization. Since families will be located all over the state of Oregon it will not be possible to mail and mail back a signed consent form in a timely way, and this delay might contaminate time-sensitive study outcomes. Therefore obtaining a signed consent in these cases is not possible.

For the expansion, we will need to obtain a HIPAA waiver to consent families off the Autism clinic waitlists. We are requesting a HIPAA waiver because it would not be possible to contact families to secure their interest in Autism ALERT without getting some information to contact them with. Having participating clinics contact families would place an unreasonable burden on clinic administrative staff, who are already overwhelmed by very long wait lists for autism services.

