informing them of the upcoming survey and the \$10 incentive for completion. A \$10 cash or gift card incentive will be provided for survey completion. The survey will initially be sent 3 times via a secure RedCap link. Then non-responders will be contacted via telephone. Subjects who do not respond to either email or telephone will be sent a survey mailing with a \$5 Dutch Bros coffee card. The survey will be marked with a study number only and will contain no personal identifiers. The study team will have a separate locked document that has the key linking study ID to personal information (see below). Completed surveys will be mailed back to the study team in an envelope and entered into a secure database behind the OHSU firewall. Original copies will be stored in a locked file cabinet in the study team area.

Study team members will also be reaching out to families via email and/or phone, about participating in a semi-structured phone interview regarding their experiences with navigators, and the overall Autism diagnosis process. Families will be contacted via email and telephone to schedule these interviews. Participating families will receive \$50 for completing the interview. Interviews will be recorded using WebEx or a digital audio recorder. These recordings will then be sent to GMR Transcription (HIPAA-compliant) to provide transcripts. Finally, the study team will code the interviews using Dedoose software to get a better understanding of parents' experiences in the Autism evaluation process.

Administrative data about children from the ecWeb (EI/ECSE) database will be governed by a Data Use Agreement (DUA) between [name] (PI) and the Oregon Department of Education (ODE). Consistent with our prior DUA's, we will request ecWeb access for only families with signed consent and a FERPA release for each child's educational data. The study team will submit names and dates of birth of people who signed consent and authorization to ODE staff, and ODE staff will allow the study team direct access to these individuals' data within ecWeb, ODE's database for Early Intervention. ODE staff are only releasing data and will not be considered engaged in research. These data include details on the dates and times of each child's referral, evaluation, and service plan. ODE staff will provide access to these data, which study team members will analyze, and are not considered part of the study team.

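### Families without internet enrol on verbal consent, but ecWeb records are requested only for families who signed, so these children drop out of the ecWeb outcomes and the protocol does not say so

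*Protocol*

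**What the plan says.** **Consent route.** Protocol section 5(f), under Families, expects electronic consent as the usual route: "In most cases, participants will provide electronic consent while on the phone with a Navigator". It then makes an exception: "For families lacking internet access, a verbal consent via telephone will be provided in lieu of electronic signed consent". It adds: "For these families we have requested a HIPAA waiver/alteration". Modifications to the Consent Process asks for a waiver of consent documentation for the same families and says: "This will allow us to obtain consent and authorization verbally for those individuals". It rejects posting forms out and back at enrolment because the delay could distort time-sensitive outcomes, and concludes: "Therefore obtaining a signed consent in these cases is not possible".

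**The interest form.** Parents sign a form at the clinic before any consent, but section 5(f) says of it: "This signed interest form signifies study interest but is not a consent for the study".

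**ecWeb access.** Section 6, Procedures, sets the rule: "we will request ecWeb access for only families with signed consent and a FERPA release". It repeats the condition for the list sent to the Oregon Department of Education (ODE): the team will "submit names and dates of birth of people who signed consent and authorization to ODE staff". The records hold the dates of each child's referral, evaluation and service plan.

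**Use of the data.** Section 8, Data Analysis, places ecWeb among the sources of secondary and exploratory efficacy outcomes. Section 4 names feasibility and acceptability as the primary outcomes of the pilot.

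**The concern.** A family that consents by telephone is a full participant, yet under section 6 its child is never on the list that goes to ODE. That child's ecWeb outcomes are then missing because of how the family consented, and consent mode follows internet access. The trial is aimed at low-income and underserved families, so this group is one the investigators want to learn about.

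The protocol provides no later signature step and no other route to ecWeb for these families, and it does not state that they are excluded from the ecWeb analyses. The waivers it describes concern consent documentation and HIPAA; neither passage that mentions them refers to the FERPA release.

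At stake are the completeness of the ecWeb outcomes and each arm's own rate or time estimate. Section 2 hypothesises more educational evaluations within six months, and ecWeb is the only source the protocol describes as holding evaluation dates. The protocol does not, however, name a source for that hypothesis, and the survey items are not shown.

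**Working it through.** There is no figure in the plan to reproduce: section 8 says the pilot is deliberately not powered. The check is a comparison of the rules, followed by arithmetic for scale.

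**Step 1: follow one family through the rules.**
- No internet: consent is verbal and replaces the electronic signature (section 5(f), Families).
- Authorization is verbal too (Modifications to the Consent Process).
- ecWeb access needs signed consent and also a FERPA release (section 6). A signed FERPA release alone would not satisfy this wording.
- The clinic interest form is signed but is not study consent, so it does not meet the condition.
- Result: enrolled, with no ecWeb dates.

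**Step 2: does the stated reason against mailed forms also rule out a later signature?** The reason is delay at enrolment. A form returned afterwards delays neither enrolment nor navigation, and it alters no date already recorded in ecWeb. The reason does not extend to it.

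**Step 3: scale.** Inputs: 25 dyads per arm (section 5(a)). The number m of verbally consented children per arm is not stated; 1, 3 and 5 are assumed. The 60% six-month evaluation rate and the 20 to 40 point gap between signed and verbal families are also assumptions.

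- Share of one arm's rate left undetermined = m/25.
- 95% half-width of the arm difference, equal loss in both arms, ignoring clustering = 1.96 × √(2 × 0.60 × 0.40 / (25 − m)).
- Error in one arm's own rate = (m/25) × gap.

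| m per arm | Undetermined | Half-width of difference | One-arm error, gap 20 to 40 points |
|---|---|---|---|
| 0 | 0 | ±27.2 points | 0 |
| 1 | 1/25 = 4 points | ±27.7 points | 0.8 to 1.6 points |
| 3 | 3/25 = 12 points | ±29.0 points | 2.4 to 4.8 points |
| 5 | 5/25 = 20 points | ±30.4 points | 4.0 to 8.0 points |

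If m and the gap are the same in both arms, the errors cancel and the bias in the arm difference is zero. Nothing in the protocol points to unequal loss.

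**The case against.** The strongest reply is that nothing here conflicts. The consent section governs enrolment and section 6 governs release of a child's education records. Asking for a signature before opening those records is a deliberate choice, which the protocol ties to its earlier data use agreements. This stands: a reader might infer a contradiction, but both rules can be obeyed at once. What remains is an unacknowledged consequence of obeying both.

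Second, the effect is undocumented and likely small. The verbal share is not given, electronic consent is expected in most cases, and every size above rests on assumed figures in a pilot whose interval for the arm difference is already about ±27 points. This also stands, and it sets the severity.

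Third, the consent forms, the FERPA release and the data use agreement are not shown and may already provide a signature for this group. That is possible, and the fix allows for it. As section 6 is worded, though, the signed condition appears twice, and Modifications to the Consent Process treats signed and verbal consent as distinct, so loose wording is not the natural reading.

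Fourth, the pilot may be over: section 4 describes a 2023 expansion without a control arm. This limits what can be recovered but does not remove the point. Section 5(f) carries verbal consent into the expansion for children referred by their primary care provider.

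**Conclusion.** The point holds, with minor severity. Followed as written, the plan leaves verbally consented children out of the secondary and exploratory ecWeb outcomes by a rule linked to internet access, and does not say so. Each such child leaves 4 points of a 25-child arm's rate undetermined; how many there are is unknown.

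Three stronger conclusions might be inferred and are not supported:
- **That the main results are affected.** The primary feasibility and acceptability outcomes do not depend on ecWeb.
- **That the comparison of arms is biased.** With similar loss in both arms the bias may be nil. A link between internet access and time to evaluation is an assumption on which the protocol gives no data.
- **That the effect sizes for the later R01 rest on ecWeb.** Section 8 describes the efficacy comparisons and effect sizes first and then adds the ecWeb and Medicaid outcomes as secondary and exploratory, analysed in the same framework. Their dependence on ecWeb dates is not stated.

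**What to change.** Keep verbal consent for enrolment. Add to section 6 that each verbally consented family is afterwards mailed a paper consent/authorization and FERPA release with a return envelope, for example with the letter already sent before the 6-month survey. State that the signed forms are valid for ecWeb whenever received before analysis. If the consent forms or the data use agreement already cover this group, a sentence in section 6 saying so is enough.

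Apply the step to pilot families already enrolled who can still be reached, and to verbally consented expansion families if ecWeb is used for them.

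The cost is a protocol amendment, a check of the data use agreement and a few mailings: 2m packs over the two pilot arms, so 2, 6 or 10 at the assumed 1, 3 or 5 per arm. Some forms will not come back, so the loss is reduced and not removed.

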## **7) Data and Specimens**

### **a) Handling of Data and Specimens**

Four types of data are collected: System Process Measures, Family-Reported Measures, PCP-Reported Measures, and Administrative Measures. Data will be stored behind an OHSU firewall on Onedrive/Sharepoint io, a contracted secure cloud storage provider. Data will be destroyed about 6 months after publication of study results. Study interest forms will be sent via fax to the study team. The website providing PCP and Navigator access will be built by the OHSU IT department in RedCap, and will have the same security as any OHSU web applications.

### **b) Sharing of Results with Subjects**

A summary of the study's findings will be shared at multiple community meetings around Oregon. As a result, some patients and providers will be notified of study results. However, we will have no consistent system for notifying patients or providers of study findings. Families who wish to receive copies of study publications can notify the study team.

An anticipated incidental finding is that children are found to have another developmental condition (instead of autism) in the context of their evaluation by Autism ALERT. We expect that this may be the case in 30-40% of children referred to the program. In these cases, the Autism ALERT navigator will connect these children to appropriate developmental resources for that condition. Because the Swindells Resource Center has expertise in a large number of developmental conditions, the navigator should have the resources to do this. In addition, the information will be communicated back to the child's PCP via the secure Autism ALERT interface.

### **c) Data and Specimen Banking**

This study will be registered at ClinicalTrials.gov upon IRB approval. Study findings will be submitted to ClinicalTrials.gov according to its submission policy. All consent materials will include a specific statement relating to posting of clinical trial information at ClinicalTrials.gov. OHSU has an internal policy in place to ensure that clinical trials registration and results reporting occur in compliance with policy requirements.

For the initial intervention only, we will also report data to the National Database for Autism Research (NDAR), which is part of the NIMH Data Archive. All consent materials will include a specific statement relating to posting of study information at NDAR. NDAR data may be used for future unspecified research. The OHSU researchers will not otherwise save or use the data for future research so there is no OHSU repository. Only data on individuals who

signed authorization for release will be submitted to NDAR and ClinicalTrials.gov; i.e. no chart review or screening data will be submitted.

## **8) Data Analysis**

Process data from CCMT and Navigator Fidelity Checklist will be used to calculate contact attempts, time to first contact, total time spent per family, and counts of specific navigator activities. Families who complete all calls will be compared to those who broke off contact, and specific points of participant drop-off will be calculated. We will assess whether specific intervention activities varied by family demographic characteristic and clinic site, to assess variability in acceptability, using bivariate analyses. Family survey data will also be used to assess feasibility and acceptability. Initial analyses will focus on families who participated in ALERT, assessing experience of care and improvement suggestions. Next, post-intervention family experience will be compared in intervention vs. control clinics using bivariate analyses with an intention-to-treat approach. We will also examine variation in experience outcomes overall, and by study arm, by demographic characteristics, in order to assess whether the intervention was appropriate for diverse families, and to target improvements. Parent responses to open-ended items will be assessed via conventional content analysis. Using the parent interviews, we will also qualitatively assess families' feelings towards the evaluation process, and for the intervention arm we will also be looking at experiences with family navigators.

PCP process data will be used in a similar fashion. PCP/Navigator interactions will be descriptively characterized, using the PCP-Navigator Con-tact log and use of the PCP Website. PCP survey data will be used to characterize PCPs' post-intervention experiences. PCPs' overall experiences will be compared in both arms using bivariate testing, and open-ended questions will be coded.

We will refine our mechanism hypotheses and measurement by examining change in family-and provider-reported outcomes (e.g., stress, empowerment) pre-and post-intervention, in both study arms, primarily using descriptive and bivariate tests. Exploratory analyses will assess whether mechanism outcomes differ by family race/ethnicity, English proficiency, or insurance type, both overall and by study arm, using bivariate or limited multivariable regression analyses. This will allow us to gather valuable descriptive data on variation in engagement of target mechanisms, which might allow for individualized messaging in future research.

We will compare efficacy outcomes in the Autism ALERT group to the baseline and control groups, using bivariate analyses and Kaplan-Meier curves for time to treatment variables. Estimated effect sizes for the subsequent R01 will be measured using Cohen's d. To test engagement of target mechanisms, we will assess whether efficacy outcomes differed by mechanistic outcome (e.g., whether parental stress was associated with time to treatment), using bivariate or limited multivariable models. We will also assess whether outcomes differ according to family demographic characteristics, both overall and by study arm, to test variability in intervention effects. Secondary and exploratory efficacy outcomes from ecWeb and Medicaid claims will be analyzed in the same framework.

Fidelity outcomes include both structural measures (e.g., receipt of program components) and procedural measures (e.g., quality of delivery of these components). We will use descriptive

statistics to assess delivery of the START Autism ± Autism ALERT training curriculum components. We will also use descriptive statistics to calculate navigator fidelity to the protocol, using the Navigator Fidelity Checklists. Checklists will also be cross-checked with recorded calls to assure accurate documentation. We will use descriptive statistics to characterize PCP use of the Autism ALERT website. To understand how Autism ALERT and START Autism altered PCP screening and referral behaviors, we will assess rate of ASD screening and EI/ECSE referral in both study arms in the baseline condition, and 3-and 6-months after initiation of START Autism ±Autism ALERT. As an exploratory analysis, we will assess whether racial/ethnic or language differences in PCP screening are present, and whether they vary by study arm or by PCP/clinic characteristics.

Our goals in this pilot study are to assess the feasibility and acceptability of the intervention and analysis, develop hypotheses regarding mechanism of action, and to provide context for defining meaningful differences and otherwise inform R01 power calculations. We intentionally have not powered to detect statistically significant differences. However, estimates will provide preliminary evidence of intervention effects, generate effect size estimates, and will help refine analytic strategy, efficacy hypotheses, and sample size estimates for a larger study.

Similar quantitative and qualitative approaches will be used for the expansion, except that there will be no control group so analyses will be primarily descriptive. We will also compare families who did versus did not engage in the Autism ALERT intervention after consenting.

**Follow Up Provider Interviews:** Analysis of the provider interviews will use a phenomenological approach. We first will use structural coding to generate a limited set of predetermined codes to categorize data broadly. This initial coding structure will be reviewed after an initial read of 2 transcripts from each respondent class. Subsequently an emergent coding approach will be used by 2-3 trained research assistants, establishing novel codes to explore each global category with greater precision, using Dedoose. A final framework will be reviewed by 2 new pediatricians for triangulation.

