## 2) Objectives

Autism Access Link for Early Referral and Treatment [ALERT], the intervention proposed in this application, is a novel state-wide referral and case management platform that PCPs can activate to ensure that a child with suspected Autism Spectrum Disorder (ASD) receives all necessary ASD diagnosis and treatment resources in a single referral, radically simplifying a complex diagnostic and treatment process. We hypothesize that Autism ALERT will have strong acceptability and high rates of use among primary care providers as well as among diverse low-income patients of children at risk for ASD, and that we will see higher rates of child ASD educational evaluations within six months, and shorter time between referral and ASD treatment,.

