## 4) Study Design

We propose a pilot clustered interventional trial with two arms. Clinics in the intervention arm receive Autism ALERT plus an ASD screening intervention (START Autism), and clinics in the comparison intervention (control) arm receive only START Autism (no Autism ALERT). As this is a pilot trial, primary outcomes of interest are feasibility and acceptability. We will additionally assess mechanism of outcome, preliminary efficacy, and protocol fidelity. Feasibility and acceptability will be assessed in intervention clinics. Mechanism of action and preliminary efficacy will be assessed by comparing intervention to control clinics. Fidelity is assessed in both arms. We will pilot test Autism ALERT in 6 safety-net primary care clinics in Oregon: 3 clinics will serve as intervention clinics, receiving both Autism ALERT and START Autism, and 3 clinics will serve as controls receiving START Autism only. Study arm will be assigned via coin-flip randomization of clinics, stratified for size and urbanicity, by a statistician who is not otherwise part of the study team.

In 2023 we received new funding from CareOregon to expand the project. As a result, this pilot study will be expanded to all of Portland-metro area. It will no longer include a control arm. Participants will be recruited off of Autism clinic waiting lists in the PDX metro area, and will be enrolled into the study to receive family navigation services from our partners at Help Me Grow.

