Families will initially receive a study packet from their provider at the time of the referral. The packet will contain a children's book, information about autism, an Early Intervention Referral Form, and a Study Interest Form. Aside from the study interest form and the phone scripts that are used for screening there are no other recruitment materials (e.g., emails, flyers) for family participants at this time. They will learn about the study first from the study interest form. The Study Interest Form will include some general information about the study, as well as a HIPAA authorization allowing disclosure of family contact information and some health information to the study team. The parent will sign the interest form, allowing the clinic to pass the family's contact information to the Navigator team. Navigators will then reach out to the family to complete the online consent process, or phone consent process as necessary (see more information below). Please see Family Consent Form attachments. Family enrollment will be incentivized with a children's book and \$50 stipend per survey completed for both experimental and control groups. Provider participants may receive Continuing Medical Education credits and/or Part IV Maintenance of Certification credits, if desired, as part of their participation in this study. Clinics may also be entered into a raffle to incentivize their patients' referral to the study, based on whether they refer any patients to the study in a given time period. The raffle incentive will be a gift or food basket costing less than \$100. Control arm clinics will also be given a box of chocolate on Valentine's day to further increase enrollment as enrollment is lagging in that arm.

For clinics in the OHSU system, referrals to the Autism diagnostic clinic will also be monitored for potential study recruitment. The diagnostic clinic staff will provide a list of MRNs of patients referred to the OHSU Autism Clinic, which will be transmitted via secure OHSU emails to the referring primary care provider and study team for inclusion in the study. Data will be transmitted as a list of MRNs, which the provider can use EPIC to identify and consider. If the provider gives permission, the study team will directly contact the family. No PHI will leave OHSU.

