key document to associate their names with their study IDs, will be sent follow-up emails, and will also be given the option to complete the survey via mail or fax. Paper surveys will be stored securely at OHSU as outlined above and destroyed approximately 6 months after publication of study results. The patient portal survey will be anonymous and no study ID or PHI will be entered. In addition to the survey, chart review data will be collected which contains information about each provider's practice patterns. These data are collected once every 3 months, in both arms. These data include number of children screened for ASD and number of children referred to EI/ECSE for an ASD concern. Note that referrals to Early Intervention are a separate process that is standard of care, and is not related to enrollment in the study. Providers will be encouraged to adhere to standard of care in terms of screening children for autism and referring to Early Intervention; however this process can be accomplished by usual methods without enrolling children in the study if providers prefer. Number of children screened for ASD, and screening test results, will be collected by a practice administrator, using an existing form that we have used in prior research projects. The administrator will be considered engaged in research through an IAA. This form will be encrypted and sent to the study team electronically using OHSU's secure server. Finally, fidelity data (e.g., PCP-Navigator Contact Log) will contain information about interactions between the PCP and the navigator. This file will be kept encrypted and stored on OHSU Box, a secure cloud server.

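### Section 8 gives no family uptake proportion: its family analyses start from enrolled or consented families, so the hypothesised rate of use cannot be tested and acceptability may be overstated

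*Protocol*

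**What the plan says.** Protocol section 4 (Study Design) states: "As this is a pilot trial, primary outcomes of interest are feasibility and acceptability". It places them at clinic level: "Feasibility and acceptability will be assessed in intervention clinics". Section 2 (Objectives) gives the hypothesis: "Autism ALERT will have strong acceptability and high rates of use among primary care providers as well as among diverse low-income patients". The patients meant there are families whose child may have ASD.

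Section 8 (Data Analysis) then names the family-level analyses:

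- Navigator process data "will be used to calculate contact attempts, time to first contact, total time spent per family, and counts of specific navigator activities".
- Families who finish all calls are compared with those who stop, and the points of drop-off are located.
- For the family survey, "Initial analyses will focus on families who participated in ALERT, assessing experience of care and improvement suggestions". Experience is then compared between intervention and control clinics by intention to treat.
- For the expansion: "We will also compare families who did versus did not engage in the Autism ALERT intervention after consenting".

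The route into the study is in section 5e (Recruitment Methods). The provider hands over a packet, the parent signs an interest form, and "Navigators will then reach out to the family to complete the online consent process", or consent by phone. Section 6 (Procedures) sends the family surveys at enrolment and six months later.

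**The concern.** A rate of use needs a denominator of families who could have used the service. Here several selection steps come before any family-level outcome. The provider may choose not to offer ALERT (section 5f), the parent may not sign the form, the family may not be reached, and a family that is reached may decline. Surveys start at enrolment, so a family lost at any of these steps gives no acceptability data. No listed analysis counts such families.

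This matters because the project is about low-income and minority families who fail to connect with services that exist for them (section 3). If the same families are harder to reach or more likely to decline, they leave before the primary outcomes are measured, and acceptability describes those who accepted. The pilot is also meant to inform a larger trial, whose planning needs reach and consent proportions.

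**Working it through.** **Is there a figure to reproduce?** There is no power, precision, uptake or acceptability figure. The protocol says that it is intentionally not powered. The only sum is the planned number of dyads in section 5a, 20 + 25 + 25 = 70, which agrees. The expansion expects around 300 children.

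**Where each family-level analysis starts.**

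| Analysis | Families it starts from |
|---|---|
| Survey, first step | Participants in ALERT |
| Survey, intention-to-treat step | Enrolled families in both arms, since surveys go out at enrolment and six months later |
| Drop-off analysis | Participants who completed calls or stopped |
| Expansion, engaged versus not engaged | Families who have consented |
| Contact attempts, time to first contact | Not stated; no proportion reached is named |

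No row brings in families who were interested or waitlisted but were not reached or declined.

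**What conditioning on enrolment could hide.** Let n be families enrolled, x those accepting, u uptake (enrolled divided by approached), and N = n/u, rounded. The true proportion accepting among all approached lies between

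- lower bound x/N (every non-enrolled family not accepting), and
- upper bound (x + N − n)/N (every non-enrolled family accepting).

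The values of u (40% to 100%) and of acceptability (88%) are assumptions. The values of n are the protocol's: 25 intervention dyads and about 300 children.

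| Uptake | Pilot N | Pilot bounds, x = 22 | Expansion N | Expansion bounds, x = 264 |
|---|---|---|---|---|
| 100% | 25 | 88% | 300 | 88% |
| 80% | 31 | 22/31 = 71% to 28/31 = 90% | 375 | 264/375 = 70% to 339/375 = 90% |
| 60% | 42 | 22/42 = 52% to 39/42 = 93% | 500 | 264/500 = 53% to 464/500 = 93% |
| 40% | 62 | 22/62 = 35% to 59/62 = 95% | 750 | 264/750 = 35% to 714/750 = 95% |

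The exact 95% interval for 22/25 is 69% to 97.5%. It reflects sampling error among enrolled families only and says nothing about those not enrolled. At 60% or 40% uptake the lower bound falls below it.

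**Adding survey non-response.** The table assumes that every enrolled family answers. Suppose instead that 90% of responders are positive, 50% to 80% of interested families are reached and consent, and 60% to 80% of those answer at six months (all assumed).

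- Low case: 0.5 × 0.6 = 0.30 of interested families respond. Positive 0.9 × 0.30 = 0.27; negative 0.03. Bounds 27% to 97%.
- High case: 0.8 × 0.8 = 0.64 respond. Positive 0.9 × 0.64 = 0.58; negative 0.064. Bounds 58% to 94%.

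The downside is large, but the direction is not fixed.

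**The case against.** Several stronger readings are tempting, and the protocol does not support them.

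- *That the primary outcomes are computed only in active participants.* The survey sentence describes a first step. The intention-to-treat comparison, the drop-off analysis and the expansion's engagement comparison include families who consented and then took up little or nothing. Asking recipients about their experience first is sensible in itself.
- *That the provider side has the same flaw.* Section 6 sends the provider survey on feasibility and acceptability to every provider in participating clinics, including those who never used ALERT.
- *That acceptability is overstated, for instance 27% to 58% instead of 90%.* Those low figures are worst cases on assumed inputs; the matching best cases are 97% and 94%. Only possible overstatement can be claimed.
- *That time to first contact is biased short.* The protocol gives no time origin and no rule for families never contacted. Navigators make contact before consent, so attempts on unreached families may be logged. Such rules may sit in a statistical analysis plan that is not shown.
- *That full denominators already exist.* For the chart review, "These data include number of children screened for ASD and number of children referred to EI/ECSE for an ASD concern". But these counts reach the team without identifiers (section 5f), and section 6 describes EI/ECSE referral as separate from study enrolment. They cannot be the first step of a nested cascade. The list of referrals to the OHSU autism clinic covers OHSU clinics only, and nothing says that packets handed out or refusals are counted.

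It is also fair that an unpowered, mainly descriptive pilot needs no elaborate analysis. What remains is that none of the listed analyses brings in families who were interested or waitlisted but not enrolled. This is more than detail left to a later plan, because the protocol itself fixes populations such as participants and families after consent.

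**Conclusion.** The point holds in a limited form. Followed as written, Section 8 yields no family uptake rate, so the section 2 hypothesis of high use among families cannot be tested, and family-level acceptability is conditional on consent. It may be overstated by an amount that the protocol does not allow anyone to compute. With an assumed 88% acceptability among enrolled families and assumed uptake of 40% to 80%, the worst case is 35% to 71% and the best case 90% to 95%; with full uptake the figure stays at 88%. The provider-side analyses are not affected. This should be changed, because it concerns the primary outcomes and the remedy is cheap.

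**What to change.** Amend Section 8 as follows.

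- **Pilot.** Report, by intervention clinic, a cascade with Study Interest Forms received as the fixed denominator: forms, reached, consented, first navigation call, all calls completed, six-month survey. Measure time to first contact from the date of the form for every form received, with unreached families censored and not dropped.
- **Expansion.** Use advance letters sent (less families found ineligible) plus provider referrals as the denominator. Count opt-outs and unreached families as non-uptake.
- **Acceptability.** Present the result among responders beside the cascade, with bounds for non-enrolled families and non-responders running from all not accepting to all accepting.
- **Chart review.** Show EI/ECSE referral counts only as a separate contextual proxy, not as the first step of the cascade.

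The forms are faxed to and kept by the team (sections 7a and 9), and the team handles the waitlist contacts, letters and opt-outs (section 5e). The cost is a small amount of extra counting and headline rates that will look less favourable.
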